4.4.2 Efficacy Endpoint

(1) Imaging Evaluation of a Target Aneurysm (O' Kelly-Marotta, (OKM))

Definition: Based on the evaluation of imaging results, the treatment of aneurysms was classified according to the following criteria. Digital Subtraction Angiography (DSA), Magnetic Resonance Angiography (MRA), or Computed Tomography Angiography (CTA) are acceptable, and it is recommended base CTA. The purpose of imaging follow-up information collection is to observe the effect of on the long-term closure of the aneurysm after treatment. Complete closure of the aneurysm would be associated with increased safety.

- No filling
- Entry remnant (<5%)
- Subtotal filling (5%~95%)
- Total filling (>95%)

The observational device with the blood flow and the aneurysm gradually closes. The evaluation results of different follow-up nodes were counted, and the time interval between the date of surgery and the aneurysm occlusion is collected.

(2) Adequate Occlusion Rate of Target Aneurysm

Definition: Adequate Occlusion is defined as Raymond-Roy Grade I or Grade II on imaging evaluation of the target aneurysm ^[5]. If the Raymond-Roy grade reaches Grade I at any evaluation point, no further imaging information will be collected. Imaging results obtained via Digital Subtraction Angiography (DSA), Magnetic Resonance Angiography (MRA), or Computed Tomography Angiography (CTA) is acceptable. The imaging results will be evaluated following the routine procedures of the clinical research institution. The post-procedure recanalization of the aneurysm is graded according to the following classification. Please refer to **Error! Reference source not found.** for Raymond-Roy Classification Standards.

Table 4-1 Raymond-Roy Classification Standards

Grade	Description
Grade I	Complete occlusion (no contrast filling in the aneurysm sac or neck)
Grade II	Neck remnant (contrast filling in the aneurysm neck but not the sac)
Grade III	Residual sac (contrast filling in the aneurysm sac)

Occlusion Rate of Target Aneurysm refers to the proportion of patients judged to be Grade 1 or Grade 2 in the total number of patients.

(3) Technical Success Rate

Definition: Technical success is defined as successful stent placement and meet following criteria:

- Stent fully cover the aneurysm neck
- Good wall apposition
- Perfusion of the parent artery
- Retention of contrast agent within the aneurysm.

The technical success rate refers to the proportion of technically successful patients in the total number of patients.

(4) Re-sheathing performance

Definition: During procedure, the observational device can be retrieved / re-sheathed into the microcatheter and re-deployed at the desired target location or removed completely from the patient. But it must not be re-deployed more than three times. Re-sheath performance refers to the retrieving and re-deploying of observational device recorded during the procedure. Information such as the number of recoveries and the number of re-sheathings, the success rate of re-opening and other information are recorded to evaluate the re-sheath performance of the observational device.

(5) Modified Rankin Scale (mRS) Change from Baseline

Definition: At different follow-up, the modified Rankin score changed from the baseline.

The modified Rankin (mRS) score was used to evaluate the improvement of neurological function. The modified Rankin score assesses the ability to live independently in patients with Neurological disease [6]. There are 7 levels of this score, 0 points represent no symptoms of disability, higher scores mean worse prognosis of patients, and 6 points represent death, See the table below for detailed scores.

Table 4-2 Modified Rankin Scale (mRS)

Score	Patient Condition
0	No symptoms of disability
1	Minor symptoms but no significant deficits; capable of all activities and work
2	Mild disability; unable to participate fully in previous activities but can live independently
3	Moderate disability; requires assistance but can walk independently
4	Moderate to severe disability; unable to walk independently, cannot live alone, requires some care
5	Severe disability; bedridden, incontinent, requires constant care
6	Death

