2.3.8 Contraindications

Use of the FRED System is contraindicated under these circumstances:

- Patients in whom anticoagulant, anti-platelet therapy, or thrombolytic drugs are contraindicated.
- Patients with known hypersensitivity to metal such as nickel-titanium and metal jewelry.
- Patients with anatomy that does not permit passage or deployment of the FRED System.
- Patients with an active bacterial infection.
- Patients with a pre-existing stent in place at the target aneurysm.
- Patients in whom the parent vessel size does not fall within the indicated range.
- Patients who have not received dual anti-platelet agents prior to the procedure.

2.3.9 Precautions and Warnings:

Please refer to Instructions for Use (IFU).

3 Clinical Study Objective

To evaluate the long-term safety and efficacy of post-marketing of Flow Re-Direction Endoluminal Device System (FRED) in the treatment of intracranial aneurysms.

4 Clinical Study Design

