4.3.4 Information of follow up

- Imaging Evaluation of a Target Aneurysm: DSA、MRA、CTA can be accepted.
- Treatment-related hospitalization information or adverse event information: Stroke, Death, Adverse Event, Serious Adverse Event.

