4.5 The Data Collection Schedule

The data collection schedule is described in

Table 4-3 Data Collection Plan

Baseline	Treatment*	Follow-Up Information**

Demographic Information¹Medical History²Physical Examination³Imaging findings⁴Modified Rankin ScaleAneurysm Information⁵Laboratory Examination⁶Information of antiplatelet function test result: platelet aggregation test/ Thromboelastographic (TEG)Information of anti-coagulation and anti-platelet medication⁷	
Using Information of DeviceInformation of ProcedureStrokeMortalityAE/SAEO'Kelly-Marotta(OKM) GradeRaymond-Roy GradeTechnical SuccessRe-sheathing Performance	
Physical Examination⁴Information of anti-coagulation and anti-platelet medication⁷Image dataLesion-Related ComplicationStrokeMortalityAE/SAE⁸O'Kelly-Marotta(OKM) GradeRaymond-Roy gradeModified Rankin Scale

Notes:

1. Demographic Information including: birth date, sex, history of smoking and drinking, ethnicity, diagnosis.
2. Medical History: Past medical history: including current medical conditions (high blood pressure, diabetes, etc.), history of cranial and neurological related surgeries, hemorrhagic stroke.

3. Physical Examination: neurological physical examination.

4. Image data collection, per standard of care (e.g., DSA, MRA, CTA) can be applied.

5. Based on CTA .

6. Laboratory Examination: Blood routine (red blood cell count, hemoglobin white blood cell count, neutrophil count, lymphocytes count, platelet count), coagulation test [Prothrombin Time (PT), Activated Partial Thromboplastin Time (APTT), Thrombin Time (TT) and Fibrinogen (FIB) International standardized ratio (INR)]. Only clinically significant abnormal results were recorded.

7. Information on anti-coagulation and anti-platelet medication: drug name, dosage and frequency of administration are needed.

*. If the same patient received other surgical treatments using observational device within the data collection time frame, only the first treatment data was selected as the baseline data, and the follow-up time was calculated at this point. The remaining surgical treatments were recorded as "concomitant surgery".

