** Each patient may have multiple follow-up information, all of which should be recorded and collected. The collected follow-up data will be divided according to the following follow-up points: 30 days after surgery, 3 months after surgery, 6 months after surgery, and 1 year after surgery, according to the principle of closest approach.

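### Imaging collection ends at the first Raymond-Roy Grade I reading, so reopening after complete occlusion cannot enter either imaging endpoint

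*Protocol*

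**What the plan says.** Section 4.4.2(2) of the protocol defines adequate occlusion as Raymond-Roy Grade I or II, over all patients, and adds a collection rule: "If the Raymond-Roy grade reaches Grade I at any evaluation point, no further imaging information will be collected". The rule speaks of imaging in general, not of the Raymond-Roy grade alone.

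Other parts of the protocol point the other way:

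- Section 4.4.2(1), on the OKM endpoint: "The purpose of imaging follow-up information collection is to observe the effect of on the long-term closure of the aneurysm after treatment".
- The same item: "The evaluation results of different follow-up nodes were counted". It also collects the time from surgery to occlusion.
- Section 4.4.2(2), shortly after the stop rule, says that recanalization after the procedure is graded on the Raymond-Roy scale.
- Section 4.5, note **: "Each patient may have multiple follow-up information, all of which should be recorded and collected". It continues: "The collected follow-up data will be divided according to the following follow-up points", and names 30 days, 3 months, 6 months and 1 year, each result going to the nearest point.
- Table 4-3 lists image data, OKM grade and Raymond-Roy grade under follow-up, with no exception for Grade I.
- Section 3 sets long-term safety and efficacy as the objective.

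Section 5.5 says that missing efficacy values will be filled by carrying the last value forward, by mean filling or by multiple imputation. It leaves the detailed rules to the SAP.

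**The concern.** Whether a later image enters the database depends on the outcome already seen. Patients with the best result leave imaging follow-up at that moment, and no later image can show whether the result lasted. Because OKM is read from the same images, both imaging endpoints are cut off together.

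The SAP cannot repair this. It can choose how to fill a gap, but it cannot recover images that were never entered. Carrying Grade I forward can only repeat Grade I. Mean filling borrows from patients who had not yet reached Grade I. Multiple imputation has no reading after Grade I from which to learn. An occlusion result at a later follow-up point therefore reflects the filling rule as well as the device, and the durability of complete occlusion, which is part of a long-term efficacy objective, goes unobserved.

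**Working it through.** **Step 1. The texts side by side.** The protocol gives no sample size, occlusion rate or reopening rate for this endpoint, so there is no figure to reproduce. The stop rule can be read as a specific exception to the general collect-everything rule of section 4.5, although the protocol does not say so. That reading removes only the conflict with section 4.5. The stated purpose of long-term closure, the counts by node and the grading of recanalization all stand in section 4.4.2 itself and remain unreconciled.

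**Step 2. What is lost and what is kept.**

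- Lost: every image after Grade I. Of the four follow-up points, at most 3, 2 or 1 are lost if Grade I is first read at 30 days, 3 months or 6 months. These are maxima, because imaging follows routine practice (Table 4-3, note 4: "Image data collection, per standard of care"). Table 4-3 also lists the Raymond-Roy grade under treatment. If that counts as an evaluation point, a Grade I reading there would remove all four.
- Kept: time to first occlusion, a rate of ever reaching Grade I or II, and worsening from Grade II to III, since patients at Grade II or III are still imaged.
- Unchanged in any case: reopening from Grade I to II, which still counts as adequate. Only reopening to Grade III changes the adequate occlusion rate.

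**Step 3. Illustration of size.** All inputs are assumptions; the documents give none.

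- g1 = share at Grade I before the 1-year point: 50-70%
- r = share of those reopening to Grade III by 1 year: 0-10%
- a = share adequate at 1 year among patients still imaged: 50%

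Formulas for the 1-year adequate rate:

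- True rate = g1(1 − r) + (1 − g1)a
- Grade I carried forward = g1 + (1 − g1)a, so the error is +g1 × r
- Mean filling from patients still imaged = g1·a + (1 − g1)a = a, so the error is a − true rate

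| g1 | r | True | Carried forward (error) | Mean filling (error) |
|---|---|---|---|---|
| 50% | 0% | 75.0% | 75.0% (0) | 50% (−25.0) |
| 50% | 5% | 72.5% | 75.0% (+2.5) | 50% (−22.5) |
| 50% | 10% | 70.0% | 75.0% (+5.0) | 50% (−20.0) |
| 60% | 0% | 80.0% | 80.0% (0) | 50% (−30.0) |
| 60% | 5% | 77.0% | 80.0% (+3.0) | 50% (−27.0) |
| 60% | 10% | 74.0% | 80.0% (+6.0) | 50% (−24.0) |
| 70% | 0% | 85.0% | 85.0% (0) | 50% (−35.0) |
| 70% | 5% | 81.5% | 85.0% (+3.5) | 50% (−31.5) |
| 70% | 10% | 78.0% | 85.0% (+7.0) | 50% (−28.0) |

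Worked row: with g1 = 60% and r = 5%, the true rate is 0.60 × 0.95 + 0.40 × 0.50 = 77%; carried forward it is 0.60 + 0.40 × 0.50 = 80%.

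The carry-forward error does not depend on a. If a is 40-60%, the mean-filling error runs from −15 points (g1 = 50%, r = 10%, a = 60%) to −42 points (g1 = 70%, r = 0%, a = 40%).

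**The case against.** The strongest defence is that the sentence is a deliberate choice that fits an endpoint about reaching occlusion. The adequate occlusion rate has no time point and uses all patients as its denominator; the OKM item collects time to occlusion; and section 4.4.3 refers to occlusion mostly occurring within 12 months. The study is descriptive, so no test is at risk. The carry-forward error rests on assumed inputs and its range includes zero. All of this is fair, and it is why the claim is confined to durability and to results at later follow-up points. It does not reconcile the rule with the long-term closure purpose or the counts by node.

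Some stronger readings are tempting but unsupported:

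- A reader might infer that reopening without symptoms would leave no trace in the study. Section 10.1.1 defines an adverse event without requiring symptoms, section 10.1.4 requires all adverse events to be recorded, and section 4.3.4 collects "Treatment-related hospitalization information or adverse event information". Reopening found on a routine scan could be recorded there, and a repeat procedure with the device would be recorded as concomitant surgery (section 4.5, note *). What is excluded is entry into the imaging endpoints.
- A reader might infer that the rate will be computed only among patients still imaged. The protocol sets the denominator as all patients and says that gaps will be filled. The figure of about 50% arises here through mean filling, which section 5.5 does list. Which listed method applies is left to the SAP, and that deferral is not itself a fault.
- A reader might expect that, without the sentence, a series with no reopening would bound the true reopening rate. Patients re-imaged in routine care after Grade I may be few and selected, so such a bound would not necessarily hold for all Grade I patients.

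**Conclusion.** The point holds in this form: the stop rule keeps any reopening after complete occlusion out of the Raymond-Roy and OKM results, against section 4.4.2's own purpose. It also makes the 1-year adequate rate depend on the filling method, in opposite directions under two of the listed methods. Both sizes rest entirely on the assumed g1, r and a. If nobody reopens, carrying forward is exact, but the images collected under this rule could not show that nobody reopened. The contradiction itself needs no assumption. It should be fixed.

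**What to change.** Delete the stop sentence in section 4.4.2(2), so that sections 4.4.2 and 4.5 and Table 4-3 agree. Enter the routine-care images of the target aneurysm that are already in the records. Report occlusion at the four follow-up points of section 4.5. Report worsening after Grade I separately, to Grade II (still adequate) and to Grade III (adequate occlusion lost), with the number of Grade I patients re-imaged and a note that they may be a selected group.

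No new scans are needed. The cost is a protocol amendment signed by the sponsor and the coordinating investigator and approved by the ethics committee before implementation (section 12), more data entry, some re-abstraction of records already entered, and a reported rate that may be slightly lower.

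If the sentence is kept, define the endpoint as first occlusion reached, state that the rule is an exception to section 4.5, and drop the long-term closure claim. That is cheaper, but gives up the durability question.

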5.5 Management of Missing and Abnormal Values

Unless otherwise specified in a specific section, the missing values of baseline and safety data will not be filled.

For the missing efficacy endpoint, the missing values will be filled by the last carry-over method, the mean filling method or the multiple imputation method, and the specific filling rules and sensitivity analysis will be detailed in the statistical analysis plan.

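### Stopping image collection at Grade I creates blanks caused by success, and two of the three fills allowed in Section 5.5 do not suit them at the later nodes

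*Protocol*

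**What the plan says.** Four statements in the protocol bear on this point.

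- Section 4.4.2, under the adequate occlusion endpoint: "If the Raymond-Roy grade reaches Grade I at any evaluation point, no further imaging information will be collected". The stop covers imaging information in general, so it removes later OKM grades as well as later Raymond-Roy grades.
- Section 4.4.2, under the OKM endpoint: "The evaluation results of different follow-up nodes were counted, and the time interval between the date of surgery and the aneurysm occlusion is collected". The Raymond-Roy rate is defined separately: "Occlusion Rate of Target Aneurysm refers to the proportion of patients judged to be Grade 1 or Grade 2 in the total number of patients". That definition names no time point.
- Section 4.5 lists both OKM and Raymond-Roy grades as follow-up information. Its note says "Each patient may have multiple follow-up information, all of which should be recorded and collected" and assigns the data to nodes: "30 days after surgery, 3 months after surgery, 6 months after surgery, and 1 year after surgery, according to the principle of closest approach".
- Section 5.5, for a missing efficacy endpoint: "the missing values will be filled by the last carry-over method, the mean filling method or the multiple imputation method". The specific rules and sensitivity analyses are left to the SAP, which is not at hand.

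No sentence says whether a grade left uncollected because of an earlier Grade I is a missing value or a known occlusion.

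**The concern.** The patients without a grade at 6 months or 1 year include everyone already recorded as completely occluded. Those who still have a collected image are, by construction, the ones who were not completely occluded at the previous node. The blanks are therefore strongly informative, and their direction is known.

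Section 5.5 nevertheless offers for them the same three methods as for an image that was simply not obtained. The methods behave very differently here. Last carry-over keeps the patient at Grade I. Filling with the node mean gives an occluded patient the average of the slower responders. Multiple imputation has to predict a later grade after Grade I, and the collected data contain no such pair.

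Section 4.4.2 gives long-term closure as the purpose of imaging follow-up. The later-node results serve that purpose, and they are the ones that depend on how these blanks are treated.

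**Working it through.** The protocol states no expected occlusion rate and no sample size, so there is no figure of its own to reproduce. The inputs below are assumptions, chosen to show direction and range.

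**Inputs (assumed).** Three curves of cumulative Grade I at 30 days / 3 months / 6 months / 1 year. Of the patients not yet Grade I, 20% are Grade II. There is no reopening and no other missing image. *Imaged* means having a collected image at the node.

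**Formulas**, per 100 patients. Let P be the number Grade I at an earlier node, C the number Grade I by this node, and II = 0.2 × (100 − C).

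- True Grade I/II rate: T = (C + II)/100
- Imaged-only rate: (C − P + II)/(100 − P). Filling each blank with the mean of the imaged patients at that node returns this same rate.
- Last carry-over: (P + (C − P) + II)/100 = T

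**Results at 1 year**

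| Curve (%) | P | New Grade I | II | True | Imaged only or node-mean fill | Shortfall | Last carry-over |
|---|---|---|---|---|---|---|---|
| 5/20/50/75 | 50 | 25 | 5 | 80% | 30/50 = 60% | 20 | 80% |
| 10/30/60/80 | 60 | 20 | 4 | 84% | 24/40 = 60% | 24 | 84% |
| 2/10/30/60 | 30 | 30 | 8 | 68% | 38/70 = 54% | 14 | 68% |

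**Results at 6 months, same curves**

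- First: true 60%, imaged 40/80 = 50%, shortfall 10 points.
- Second: true 68%, imaged 38/70 = 54%, shortfall 14 points.
- Third: true 44%, imaged 34/90 = 38%, shortfall 6 points.

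On all three curves the shortfall grows from 6 months to 1 year.

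**Direction.** With p = P/100 and T as a proportion, the shortfall is T − (T − p)/(1 − p) = p(1 − T)/(1 − p). It is positive whenever someone reached Grade I earlier (p > 0) and not everyone is adequately occluded (T < 1). First curve at 1 year: 0.5 × 0.2/0.5 = 0.20. The direction does not depend on the chosen curve; only the size does.

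**Other inputs.** With 10/25/50/70% and 20% Grade II, the 1-year figures are 26/50 = 52% imaged against a true 76%, a shortfall of 24 points. Raising Grade II to 40% of the rest gives 32/50 = 64% against 82%, or 18 points. Both fall within the range above.

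**Multiple imputation.** No patient with an earlier Grade I has a later collected grade. A model that includes the earlier grade cannot estimate its effect at Grade I from these data. A model that omits it borrows from patients not yet occluded. In a simulation of the three curves using one baseline covariate only, the Grade I/II results were 71.2%, 71.8% and 63.0% against true 80%, 84% and 68%, so 5 to 12 points low. The protocol does not prescribe that model, so these figures are illustrative.

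**Reopening.** If a share r of earlier Grade I patients is no longer Grade I or II, last carry-over is too high by p × r. With p = 0.5 and r = 2%, 5% and 10%, the excess is 1, 2.5 and 5 points. On the first curve that is 80% reported against a true 79%, 77.5% and 75%.

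**The case against.** The best reply is that the protocol already permits the right answer. Section 5.5 says missing efficacy values will be filled, it lists last carry-over first, and that method has no bias when closure is durable. The choice among the three is left to the SAP, and SAP detail is not a protocol defect. This stands in part: the protocol leaves the result open and does not force a low one.

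It follows that three stronger readings are not supported.

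- A reader might infer that, applied as written, the 1-year rate drops to new occlusions over all patients: 30/100 on the first curve, down from 40/100 at 6 months. That needs the blanks to be left unfilled and counted as failures, which is not what Section 5.5 says.
- A reader might infer that Grade I patients are not imaged again. The study is retrospective, and the rule stops collection of data, not imaging in routine care.
- A reader might infer that the Raymond-Roy rate is certainly a node rate. Its definition names no time point and could mean Grade I or II at any evaluation, which loses nobody. Node counting is written under OKM. Section 4.5, however, divides all follow-up data by node, Raymond-Roy grades included, and the protocol does not state the any-evaluation reading.

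It can also be said that the interval from surgery to occlusion is collected, so later status can be derived if closure lasts. That is true and makes the remedy easy, but no sentence in the protocol says to do it.

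Deferral to the SAP does not dispose of the point. The protocol itself fixes both the stop rule and the list of fills. Whether these blanks are missing at all is part of the endpoint definition, and no SAP can recover images that were never collected.

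**Conclusion.** The point holds as a gap in the endpoint definition combined with too wide a list of fills. The stop at Grade I produces later blanks because of success, and Section 5.5 does not set them apart from ordinary missing values. Filling with the node mean, or analysing imaged patients only, would put the 1-year Grade I/II rate about 14 to 24 points too low with no reopening. Multiple imputation would rest on extrapolation for exactly these patients. Last carry-over is correct under durable closure and 1 to 5 points too high if 2 to 10% of earlier Grade I patients reopen, when half the cohort was Grade I before the node.

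The sizes rest on assumed occlusion curves, a 20% Grade II share and complete imaging otherwise. The direction for mean filling and imaged-only analysis does not rest on the particular curve. The documents do not show that the planned analysis will be biased, since the SAP may choose last carry-over. They show that the protocol allows choices that would be.

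**What to change.** 1. **Section 4.4.2.** State that, at a follow-up node, a patient with an earlier Raymond-Roy Grade I and no later collected image counts as Grade I (for OKM, the last recorded grade) and stays in the denominator. Report the number carried in this way beside the number imaged at the node.
2. **Section 5.5.** State that values left uncollected because of an earlier Grade I are not filled by mean filling or multiple imputation.
3. **Sections 4.4.2 and 4.5.** Reconcile the collection stop with the instruction to collect all follow-up information, so that routine images that exist after Grade I are collected and replace the carried value. Without this step no replacement image could enter the database.

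The cost is a few sentences in the protocol, matched in the SAP, and one table column. Step 3 adds some abstraction from existing records and asks for no new imaging. A carried Grade I still assumes durable closure; the split between carried and imaged patients shows how much of each rate depends on that.

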Endpoint	
Safety Endpoints[Adjudicated by Clinical Event Committee (CEC)]
 
1) stroke Rate2) All-cause Mortality3) Lesion-Related Symptoms or Signs Rate4) Lesion-Related Complication Rate (Immediate post-procedure)5) Adverse Event (AE), Serious Adverse Event (SAE)
Statistical Analysis Method	
Efficacy Endpoints
 
1) Imaging Evaluation of Target Aneurysm [O'Kelly-Marotta(OKM) Grade]2) Adequate Occlusion Rate of Target Aneurysm (Base Raymond-Roy Grade)3) Technical Success rate (Immediate post-procedure)4) Re-sheathing Performance (Immediate post-procedure)5) Modified Rankin Scale (mRS) Change from Baseline 
Sample Size Estimation This study is an observational study that does not involve statistical hypotheses. Therefore, the plan is to collect data on as many patients as possible who received FRED treatment for intracranial aneurysms in China from May 2023 to May 2027, and as such, there is no specific sample size estimation.
 
Statistical Analysis Datasets The dataset will consist of all study patients who meet the inclusion and exclusion criteria.
 
General Principles of Statistical Analysis Detailed information on statistical analyses will be described in a separate Statistical Analysis Plan (SAP), with the final version of the SAP to be completed prior to database lock. The statistical analysis will be performed for this study using SAS® (version 9.4 or

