4.2.2 Exclusion Criteria

Patients who met the inclusion criteria at all time points were required to be included in the study. Therefore, no specific exclusion criteria were set.

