4.3.3 Information of Procedure

• Before Procedure

- Aneurysm Information (Target): aneurysm location (left/right, C2 petrous segment-C7 terminus), aneurysm size (aneurysm maximum diameter, aneurysm neck width, dome to

neck ratio) and morphology (saccular aneurysm, dissecting aneurysm, fusiform aneurysm), ruptured / unruptured / recurrent and the diameter of the parent artery (Base CTA).

- Laboratory Examination(Clinically significant abnormal results only, that means abnormal laboratory test results that were judged by the investigator to be different from the normal standard values and had certain reference value for the diagnosis of clinical diseases).
- Information of Antiplatelet Function Test Result: platelet aggregation test/thromboelastographic (TEG).
- Information of anti-coagulation and anti-platelet medication: drug name, dosage and frequency of administration are needed.

- **Using Information of Device**

- Microcatheter: product name, model, size
- Coil Usage: Yes/No and number
- Balloon: Yes/No and number
- FRED: number, model, lot number FRED:

- **Information of Procedure**

- Puncture position (femoral artery/radial artery, left/right)
Re-sheathing Performance: Whether re-sheathing after release, re-sheathing times, re-sheathing success or not
- Imaging results of immediate post-operation: stent fully cover the aneurysm neck, good wall apposition, parent artery perfusion, retention of contrast media.
- Procedure complication: Complications of arterial puncture including pain, local bleeding, or injury to the artery, or adjacent nerves. Dissection or perforation of the parent artery, Rupture or perforation of the aneurysm, Vasospasm, Stent thrombosis.

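### Technical success requires contrast to be retained in the aneurysm, so a well-placed device with an aneurysm that no longer fills at the end of the procedure is scored as a failure

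*Protocol*

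**What the plan says.** Protocol section 4.4.2(3) opens its definition with "Technical success is defined as successful stent placement and meet following criteria". Four items follow: coverage of the neck, apposition to the vessel wall, flow in the parent artery, and "Retention of contrast agent within the aneurysm". No alternative is attached to the fourth item. The rate is fixed in the same section: "The technical success rate refers to the proportion of technically successful patients in the total number of patients". The Synopsis places the endpoint immediately after the procedure.

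Section 4.4.2 also defines two occlusion scales. Table 4-1 gives Raymond-Roy Grade I as "Complete occlusion (no contrast filling in the aneurysm sac or neck", and the best OKM category is no filling. Adequate occlusion in 4.4.2(2) is Grade I or II. The Treatment column of Table 4-3 (section 4.5) lists the OKM grade, the Raymond-Roy grade and technical success together.

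Adjunctive coils are foreseen. Section 4.3.3 records "Coil Usage: Yes/No and number". Section 4.2.2 says "Therefore, no specific exclusion criteria were set", so coiled patients stay in the denominator.

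**The concern.** Retention of contrast is a sign that flow in the aneurysm has slowed. It presupposes that contrast still gets in. Where the aneurysm no longer fills, there is nothing to retain, and the fourth criterion fails for a reason that has nothing to do with poor placement. The patient is then a failure on one efficacy endpoint and a best-grade success on another at the same time point.

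Section 4.4.3 names the technical success rate among the indicators that the regulator requires. Because the study is descriptive, the rate and its exact confidence interval (section 5.3.4) are themselves the result. A numerator that leaves out a group with the best immediate grade passes straight into what is reported.

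There is also a coding problem. A site facing a non-filling aneurysm has no instruction on how to complete the retention item in 4.3.3. One site may enter no, and another may enter yes because the result is good.

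**Working it through.** The protocol states no technical success rate, target or sample size, so there is no figure to reproduce. The check is one of logic, followed by simple arithmetic.

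**Step 1: the definitions side by side.** Take a patient whose stent covers the neck, lies well against the wall and leaves the parent artery open, and whose aneurysm does not fill at the end of the procedure.

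| Endpoint | Rule | Result |
|---|---|---|
| Raymond-Roy (Table 4-1) | No contrast in sac or neck | Grade I, the best |
| OKM, 4.4.2(1) | No filling | Best category |
| Adequate occlusion, 4.4.2(2) | Grade I or II | Success |
| Technical success, 4.4.2(3), criteria 1 to 3 | Coverage, apposition, parent-artery flow | Met |
| Technical success, 4.4.2(3), criterion 4 | Contrast retained in the aneurysm | Not met |
| Technical success overall | Placement and the listed criteria | **Failure** |

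No other section alters this result.

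**Step 2: the ceiling.** Let c be the share of patients with no filling at the end of the procedure. Every one of them fails criterion 4, so

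maximum technical success rate = 1 - c.

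The protocol does not give c. Assumed range 0% to 20%:

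- c = 0: ceiling 100%, no effect
- c = 5%: 1 - 0.05 = 95%
- c = 10%: 1 - 0.10 = 90%
- c = 20%: 1 - 0.20 = 80%

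**Step 3: the rate before and after a change of wording.** Let s be the share meeting every requirement except criterion 4, and assume that the same share c of these patients does not fill. Assume also that all those who do fill retain contrast. Then the rate as written is s x (1 - c). If no filling also satisfied criterion 4, the rate would be s. With s assumed to be 98%:

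| c (assumed) | As written, s x (1 - c) | If no filling also counts | Difference, s x c |
|---|---|---|---|
| 0% | 98.0% | 98.0% | 0 |
| 5% | 0.98 x 0.95 = 93.1% | 98.0% | 4.9 points |
| 10% | 0.98 x 0.90 = 88.2% | 98.0% | 9.8 points |
| 20% | 0.98 x 0.80 = 78.4% | 98.0% | 19.6 points |

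Both s and c are assumptions. The logic of step 1 does not depend on them.

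**Step 4: who is affected.** Only patients whose aneurysm does not fill. A coiled patient whose aneurysm still holds contrast passes criterion 4 as written.

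**The case against.** The strongest reply is that the criterion suits this device. Section 4.4.2(1) describes gradual closure, section 4.4.3 places most occlusion within 12 months of treatment, and section 2.1.2 gives the mechanism as stagnation followed by thrombosis. For a flow diverter used alone, retained contrast is a sensible immediate sign that it is working, and immediate non-filling may be uncommon. This stands. The criterion itself is sound, and what is missing is a rule for the case it does not fit.

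A second reply is that the sponsor probably meant retention or no filling, and that the word *all* does not precede the list. Both may be so. But the sentence joins placement to the listed criteria without alternatives, and the natural reading requires each of them. Nor is this a detail left to the statistical analysis plan. That plan, which is not at hand, may refine the derivation, but the protocol states the definition and its result is wrong for this group.

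A third reply is that the damage is limited. There is no hypothesis (section 5.1) and no pass mark (section 5.6), and affected patients can be found from the grades and coil field already recorded. This stands too, and it lowers the severity.

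A reader might infer a large bias. Assuming, for example, that 20% to 50% of patients are coiled and 30% to 50% of those do not fill gives 0.20 x 0.30 = 6% to 0.50 x 0.50 = 25% of patients affected. The protocol supports none of these inputs. A yes/no coil field shows that coils are possible, not that they are frequent or stop filling at once. The range has to start at zero. A reader might also infer that the rate will differ between centres according to their use of coils. That could happen, but the protocol says nothing about coil use by centre.

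**Conclusion.** The point holds as a defect in a stated definition. As written, section 4.4.2(3) classes a correctly placed device with immediate complete occlusion as a technical failure, and it caps the rate at 1 - c. The size cannot be found from the protocol: it is nil if no aneurysm is free of filling at the end of the procedure, and the ceiling falls by 5, 10 or 20 points if c is assumed to be 5%, 10% or 20%. The conclusion rests on reading the four items as jointly required and on the two occlusion grades being taken at the end of the procedure, as Table 4-3 indicates.

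The severity is moderate to minor. The study is descriptive, the endpoint is one of five efficacy endpoints with no stated ranking, and the affected patients can be identified from planned data. The text does not support calling the whole endpoint invalid or claiming a known, material bias.

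**What to change.** In section 4.4.2(3), reword the fourth criterion along these lines: *contrast is retained within the aneurysm, or the aneurysm does not fill (Raymond-Roy Grade I / OKM no filling), at the end of the procedure*. Derive it from the immediate grades already collected, and say in the derivation rule which grade governs if the two disagree. The other three criteria still apply, so a non-filling aneurysm with a closed parent artery would remain a failure.

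Leave the retention item in section 4.3.3 as its own raw field. Merging no filling into it would hide which of the two was observed.

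Showing the rate by coil use is optional. It would let readers see how far non-filling goes with coiling, since non-filling after coils is not in itself evidence of flow diversion.

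The cost is one changed sentence and one derivation rule, with no new data. If the protocol already has ethics approval, section 12 requires the change to be signed and approved before use. Making it before the first period in section 5.4 is analysed would keep all three periods on one definition.
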